## Drug Dilution Methods:

• Use 250 mL of sterile physiological saline (0.9% sodium chloride solution) to dilute the total dose of the drug to be administered.

## Drug Use Instructions:

- CS1001 is administered by intravenous infusion rather than IV bolus.
- Ensure that the study drug solution is clear, transparent, and free of visible particles.
- Draw the study drug injection with a syringe. The volume of the injection is 40 mL (3 mL/bottle: 13.33 bottles, or 20 mL/bottle: 2 bottles; do not mix the two strengths of injections during one infusion configuration). Inject it into a 250 mL saline intravenous infusion bag.
- Turn upside-down **gently** when mixing, and prohibit shaking.
- Visually inspect the prepared solution. If it is not clear or has precipitation, the solution should be discarded and be recorded in the responsibility log of drug management.
- Record the time and the corresponding dose (in mg) of CS1001 on the intravenous infusion bag label.
- The infusion of the study drug should be completed within **60 120 minutes.** According to Section错误!未找到引用源。, if the infusion reaction occurs, the infusion time can be prolonged. Do not use the same infusion intravenous catheter while administering other drugs.
- At the end of infusion, the infusion tube should be rinsed with a sufficient amount of saline.
- It is recommended that the study drug should be given to the subject immediately after preparation to avoid exposure of the prepared drug to room temperature over the recommended **6-hour limit**. Among them, the 6-hour time limit includes storage time of DP bottles at room temperature, storage time of infusion solution in the intravenous infusion bag and infusion duration. If you need to delay the use of prepared drugs, you can place it in a refrigerator (2-8 °C), but not more than **24** hours.

## 6.2.3. Return and Destruction of Study Drugs

In this study, the study drug will be recovered. All unused and/or partially used study drugs

will be returned to the sponsor-designated third party for destruction upon completion of

complete accountability records at the study site (please refer to the drug manual and corresponding instructions for specific instructions on drug distribution, accountability and recovery). Relevant personnel of the trial shall ensure that the disposal of study drug is reasonably arranged, appropriate handling procedures are formulated according to applicable regulations, guidelines and rules and regulations, and relevant records are made. Study drugs will be destroyed after approval of the sponsor.

## 6.3. COMPLIANCE TO STUDY TREATMENT

• BLU-554

Subjects will be dispensed the appropriate number of study drug bottles to allow for dosing for a full cycle, or until the next scheduled visit. Subjects are to bring back all unused capsules (or the empty bottles) on D1 of each treatment cycle or at the next scheduled visit. Compliance with the dosing regimen will be assessed based on brought back of unused drug (or empty bottles).

• CS1001

In order to ensure the treatment compliance, the dosage will be monitored by the primary investigator or his/her designees. Accurate medication (at the initiation and end of the infusion) time and dosage should be recorded. If the infusion is interrupted, the cause of the interruption must also be recorded in the eCRF.

• Overdose

An overdose is defined as: the subject (intentionally or accidentally) takes a drug dose that exceeds 20% of the protocol specified dose. Subjects who are suspected to have an overdose must receive appropriate supportive care as determined by the investigator and medical monitor after consultation. Any adverse event resulting from an overdose should be reported to the medical monitor and included in the standard adverse event report.

## 6.4. STUDY TREATMRNT ADJUSTMENT

These guidelines should be followed by clinical Investigators, however, for an individual subject, dose interruptions, reductions, and treatment discontinuation should also be based on the clinical circumstance. Deviation from these guidelines must be documented and communicated with the sponsor. Adverse events are to be graded according to NCI CTCAE version 5.0.

- For the Phase Ib dose escalation, dose reductions for BLU-554 during the evaluation period of DLTs are only allowed if a DLT is observed.
- Dose reduction is not permitted for CS1001. If a subject experience a CS1001 related toxicities, then the subject must suspend or permanently discontinue CS1001 treatment.
- During the study treatment, if Investigator can judge AE is associated with one of the investigation products, the IP can be suspended, another IP could continue to be administrate. If cannot judge, both of the IPs should be suspended.
- If the study treatment is delayed according to the scheduled administration time for any reason (BLU-554 interrupted 2 weeks, CS1001 interrupted 9 weeks), the study treatment will no longer continue to be given (if the investigator considers that the subject is still benefiting, the subject may continue to receive the treatment with the consent of the medical monitor, i.e. the sponsor).
- Two administration delays are allowed due to toxicity. If the need for third delayed

administration of toxicity occurs, after consultation with the sponsor, the study treatment will be permanently terminated.

- 6.4.1. BLU-554 Dose Modifications
  - Any Grade 1 or Grade 2 BLU-554-related AE no dose modification required
  - Any Grade 3 or Grade 4 BLU-554-related AE, suspend (for at most 2 weeks) until event is ≤ Grade 1, or has returned to baseline, then resume by reducing 1 dose level. (if returned to ≤ Grade 1 or baseline within 14 days, and Investigator believes that it is in the subject's best interest, treatment may resume without dose reduction, with the written approval of the sponsor). If not resolved or returned to ≤ Grade 1 or baseline within 14 days, subjects should discontinue the treatment with BLU-554.
  - After reducing the dose of BLU-554 due to BLU-554-related adverse events, subjects should maintain such reduced dose during the subsequent treatment. The dose can be reduced as low as 300 mg.

\* In case immune mediated etiology cannot be excluded; consider following the guidelines in Section 14.3.

6.4.2. CS1001 Dose Suspension

CS1001 will be **suspended** for any of the following CS1001-related adverse reactions:

- Any Grade  $\geq 2$  non-skin, drug-related adverse event, with the following exceptions:
  - Grade 2 drug-related fatigue or laboratory abnormalities do not require a treatment delay
  - Grade 2 drug-related hypothyroidism/hyperthyroidism do not require a treatment delay
- Any Grade 3 skin, drug-related adverse event
- Any Grade 3 drug-related laboratory abnormality, with the following exceptions:
  - Grade 3 lymphopenia does not require dose delay
  - For a subject who has Grade  $\geq 2$  drug-related AST, ALT, or total bilirubin elevation, dose delay is required
  - Any Grade ≥3 drug-related amylase or lipase abnormalities not associated with symptoms or manifestations of pancreatitis do not require dose delay. If such Grade ≥ 3 amylase or lipase abnormalities occur, the sponsor's medical monitor should be consulted
- Any adverse event, laboratory abnormality, or intercurrent illness which, in the judgment of the investigator, warrants delaying the dose of CS1001.

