## 6.4.4. CS1001 Permanent Discontinuation

Subjects will be required to permanently discontinued CS1001 for the following drug relatedadverse events:

- Any Grade 2 CS1001-related uveitis, eye pain or blurred vision that does not respond to topical therapy and does not improve to Grade 1 severity within the re-treatment period OR requires systemic treatment.
- ≥ Grade 3 infusion-related reaction during or after CS1001 infusion see Section 错误!未找到引用源。
- Grade 3-4 severe pneumonitis
- Any Grade 3 non-skin, drug-related adverse event lasting > 7 days, with the following exceptions:
  - Grade 3 drug-related uveitis, pneumonitis, bronchospasm, hypersensitivity reaction, or infusion reaction of any duration requires discontinuation.
  - Grade 3 drug-related endocrinopathies adequately controlled with only physiologic hormone replacement do not require discontinuation.
  - Grade 3 drug-related laboratory abnormalities do not require treatment discontinuation except:
    - Grade 3 drug-related thrombocytopenia >7 days or serious uncontrollable bleeding event requires discontinuation;
    - any drug-related liver function test (LFT) abnormalities that meet the following criteria requires discontinuation:
      - AST or ALT > 5-10  $\times$  ULN for 2 weeks
      - AST or ALT  $> 10 \times ULN$
      - Total bilirubin  $> 5 \times ULN$
      - Concurrent AST or ALT >  $3 \times$  ULN and total bilirubin >  $2 \times$  ULN
- Any Grade 4 drug-related adverse event or laboratory abnormality, except for the following events which do not require discontinuation:
  - Grad4 neutropenia  $\leq$  7 days

- Grade 4 lymphopenia or leukopenia
- Isolated Grade 4 electrolyte imbalances/abnormalities that are not associated with clinical sequelae and are corrected with supplementation/appropriate management within 72 hours of their onset.
- Grade 4 drug-related endocrinopathy adverse events, such as adrenal insufficiency, ACTH deficiency, hyper- or hypothyroidism, or glucose intolerance, which resolve or are adequately controlled with physiologic hormone replacement (corticosteroids, thyroid hormones) or glucose-controlling agents, respectively, may not require discontinuation after discussion with and approval from the sponsor Medical Monitor.
- Any event that leads to delay in dosing lasting > 9 weeks from the scheduled dosing requires discontinuation, with the following exceptions:

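### Protocol 6.4.2 and 6.4.4 are inconsistent on CS1001 for a Grade 4 amylase or lipase abnormality without pancreatitis manifestations

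*Protocol*

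**What the plan says.** Protocol 6.4.2 lists the CS1001-related events for which dosing is suspended. One bullet covers "Any Grade 3 drug-related laboratory abnormality, with the following exceptions". Among the items under it is this one, written for any abnormality of Grade 3 or higher: "drug-related amylase or lipase abnormalities not associated with symptoms or manifestations of pancreatitis do not require dose delay". The next sentence says that if such Grade 3 or higher "amylase or lipase abnormalities occur, the sponsor's medical monitor should be consulted". No suspension or discontinuation is attached to the event in that section.

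Protocol 6.4.4 lists the events that end CS1001 for good. Its lead-in is mandatory: "Subjects will be required to permanently discontinued CS1001 for the following drug"-related events listed there. One item is "Any Grade 4 drug-related adverse event or laboratory abnormality, except for the following events which do not require discontinuation". Four exceptions follow:

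- "Grad4 neutropenia" lasting 7 days or less
- "Grade 4 lymphopenia or leukopenia"
- isolated electrolyte abnormalities without clinical sequelae that are corrected within 72 hours
- controlled endocrinopathies, after agreement with the medical monitor

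Amylase and lipase do not appear in that list.

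**The concern.** A site with a CS1001-related Grade 4 amylase or lipase value and no manifestations of pancreatitis finds one section that exempts the event from any dose delay and another that requires CS1001 to be stopped permanently. Neither refers to the other.

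The handling also feeds reported results. Discontinuation of study drug is a named tolerance endpoint, primary in Phase Ib and secondary in Phase II (Protocol 3.1 and 3.2). The SAP counts subjects who ended each drug, with reasons (3.3.1), and adverse events leading to discontinuation (3.5.3). With 20 sites planned, the same event could be handled and counted differently for reasons that have nothing to do with tolerability.

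**Working it through.** The plan gives no figure on this point to reproduce, so the check is mainly a comparison of text.

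**1. Does the 6.4.2 exemption reach Grade 4?** Its parent bullet names Grade 3 only. The exemption itself is written for Grade 3 or higher, and the consultation sentence repeats that range. The neighbouring lymphopenia exemption is written for Grade 3 alone, and Grade 4 lymphopenia is then exempted separately in 6.4.4. Amylase/lipase is the only exemption under that bullet that goes beyond Grade 3, and it has no counterpart in 6.4.4.

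**2. Does 6.4.4 exempt the event at Grade 4?** No. None of the four exceptions covers a pancreatic enzyme.

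**3. The two sections by grade**, for a CS1001-related amylase or lipase abnormality without pancreatitis manifestations:

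| Grade | 6.4.2 | 6.4.4 | Consistent? |
|---|---|---|---|
| 3 | No delay required; consult monitor | No discontinuation: Grade 3 laboratory abnormalities are exempt apart from the thrombocytopenia/bleeding and liver-test criteria | Yes |
| 4 | No delay required; consult monitor | Permanent discontinuation | No |

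**4. Does another section settle it?**

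- Section 6.4 allows clinical circumstance to be weighed, but requires departures from the guidelines to be documented and communicated to the sponsor. It does not rank the two sections.
- Section 6.4.3 does not mention either enzyme.
- Appendix 3 requires discontinuation for pancreatitis as an immune-related event at Grade 3 or higher. That concerns pancreatitis, not an enzyme rise without it.
- The first bullet of 6.4.2, on non-skin events of Grade 2 or higher, exempts laboratory abnormalities only at Grade 2. So 6.4.2 is not fully consistent within itself either.

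**5. How would the event come to light?** The panel in 7.1.5 contains neither enzyme. The schedule footnotes allow extra safety tests when clinically indicated, so any value would come from an unscheduled test.

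**6. Size per affected subject.** SAP 3.1 summarises Phase II in aggregate. Protocol 4.1 plans about 25 FGF19 IHC+ and 15 IHC- subjects: 25 + 15 = 40.

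- Both groups enrolled: 1/40 = 2.5 percentage points.
- IHC- group not opened and no IHC+ extension: 1/25 = 4 percentage points.

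These show only how far one case moves the rate. How many cases to expect cannot be derived from the documents.

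**The case against.** The strongest reply is that the sections regulate different actions. Section 6.4.2 governs suspension: saying that a delay is not required removes one trigger for a pause and does not order the site to keep dosing. Section 6.4.4 governs discontinuation and applies on its own terms, so a site working through both could reach a single answer.

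Part of this stands. A reader might infer that 6.4.2 positively instructs continued treatment. It does not, and its last bullet lets the investigator delay CS1001 for any laboratory abnormality. The reply does not remove the inconsistency, though. If 6.4.4 always governs at Grade 4, the Grade 4 part of the 6.4.2 exemption has no effect, because exempting a subject from delay means nothing once treatment has ended. The consultation would also have nothing to decide. Where 6.4.4 intends the monitor to have discretion at Grade 4, as for endocrinopathies, it says so.

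Three further objections limit the impact, and they are right:

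- The event goes to the medical monitor under 6.4.2, so it should reach the sponsor and not depend wholly on which section a site happens to read.
- The conflict needs an unscheduled test, a Grade 4 value, attribution to CS1001 and no pancreatitis manifestations. A test ordered because pancreatitis is suspected will often come with symptoms, and the exemption then does not apply.
- Tolerance in Phase II is a secondary, descriptive endpoint; the primary endpoint is objective response rate.

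**Conclusion.** The inconsistency is real and confined to Grade 4. Its reach is small and its frequency unknown. One affected subject would shift the Phase II CS1001 discontinuation rate by about 2.5 percentage points on 40 subjects, or 4 points on 25 if the IHC- group is not opened and no subjects are added.

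A reader might infer that the Phase Ib primary tolerance endpoint or the dose choice is in doubt. The documents do not support that. Protocol 4.3.1 records that Phase Ib recruitment finished on May 20, 2020 and that the recommended dose was confirmed on June 18, 2020, so clarifying this text now would have little bearing on Phase Ib. Nor do the documents support a claim that the Phase II discontinuation rate is materially distorted, since nothing in them indicates that any such case is expected.

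The conclusion rests on two assumptions. The first is that the abnormality is judged CS1001-related, which both sections presuppose. The second is that a Grade 4 value can occur without pancreatitis manifestations under CTCAE v5.0. The protocol's wording implies that it can, but the grading table is not reproduced in the documents and this was not checked.

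**What to change.** Reconcile Protocol 6.4.2 and 6.4.4 so that a single instruction applies to a Grade 4 drug-related amylase or lipase abnormality without pancreatitis manifestations, and so that the grade range in the 6.4.2 exemption agrees with its parent bullet and with 6.4.4. In doing so, the sponsor should confirm that such a Grade 4 event can arise under the grading version in use. Which clinical rule should apply is for the sponsor and investigators; none is proposed here.

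The cost is about one line of protocol wording, which can go into the next amendment. No change to the SAP, the sample size or the schedule of assessments follows from it.

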## 6.4.3. CS1001 Dose Resumption

Subjects may resume treatment with CS1001 when the CS1001-related AE(s) resolve to Grade  $\leq 1$  or baseline within 9 weeks from the scheduled dosing, with the following exceptions:

- Subjects may resume treatment in the presence of Grade 2 fatigue.
- Subjects who have not experienced a Grade 3 drug-related skin AE may resume

treatment if the event recovers to Grade  $\leq 2$  skin toxicity.

- Subjects with combined Grade 2 AST/ALT and total bilirubin values meeting discontinuation parameters should have treatment permanently discontinued.
- Drug-related pulmonary toxicity, diarrhea, or colitis must be completely resolved to baseline level before treatment is resumed. For patients with Grade 1 pneumonitis despite steroid tapering for at least 1 month, treatment may be resumed after discussion with and approval by the sponsor's medical monitor.
- Drug-related endocrinopathies adequately controlled with only physiologic hormone replacement may resume treatment after consultation with the sponsor medical monitor.

Two dose delays are allowed due to toxicity. If the need for third delayed administration of toxicity occurs, after consultation with the sponsor, the study treatment will be permanently terminated.

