6.6.3. Immune-Related Adverse Events

If an immune-mediated AE is suspected, the investigator should ensure that the evidence of etiology is conclusive or other causes may be excluded.

For any irAE of  $\geq$  Grade 3 or irAE of Grade 2 with the requirement of drug suspension or permanent withdrawal, the investigator should inform the sponsor as soon as possible and consult with the sponsor if necessary.

Based on the severity of AE, CS1001 will be suspended and corresponding treatment will be given. For subjects who use corticosteroids, corticosteroid dose will be gradually reduced within at least 1 month after the adverse reaction is improved to grade 1 or better. Short-term immunosuppressive agents such as tumor necrosis factor antagonists, mycophenolate mofetil or other drugs may be used if needed. If the severity of AE is maintained at grade 1 or better, CS1001 treatment can be restarted. In the event of an immune-mediated persistent, worsening or recurrent adverse event of Grade 3, or an immune- mediated event of Grade 4, CS1001 treatment should be discontinued permanently. For the identification, diagnosis, management and dose adjustment of irAE, please refer to APPENDIX 3: GUIDANCE FOR IMMUNE-RELATED ADVERSE REACTIONS MANAGEMEMT

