	pruritus, skin	identified, it	corticosteroids and	
	ulceration,	should be	oral over-the-counter	
	bullous	considered	antihistamines and	
	dermatitis,	immune-related	systemic	
	Stevens-Johnson	Pathologic	corticosteroids if no	
	syndrome	evaluation of	improvement within 7	
		skin biopsy can	days	
		be performed to	Severe (Grade 3, >	Withhold the
		rule out	30% of body surface	administration of
		alternative	area): administration	CS1001 until
		etiology	of corticosteroids at a	resolved to $\leq$
			dose of 1-2 mg/kg/day	Grade 2
			prednisone equivalents	

1	1		Life-threatening	Permanent
			e	
			(Grade 4, Stevens-	discontinuation
			Johnson syndrome,	from the study
			toxic epidermal	
			necrosis, full-thickness	
			dermal ulceration,	
			necrosis or	
			hemorrhage): high	
			dose corticosteroids	
			(2-4 mg/kg/day IV	
			methylprednisolone);	
			in-patient	
			hospitalization;	
			consultation with a	
			dermatologist	
Neuromuscular	Peripheral	Physical exam	Moderate (≤ Grade 2):	Withhold the
toxicity	sensory	~	administration of	administration of

irAE	Potential signs and symptoms neuropathy, muscle weakness, Guilliain-Barre syndrome, transverse myelitis,	Diagnosis and differential diagnosis of sensory change, loss of deep-tendon reflexes • Neuroimaging, nerve conduction	Recommended management corticosteroids at a dose of 1-2 mg/kg/day prednisone equivalents Severe (≥ Grade 3): high dose corticosteroids (2-4 mg/kg/day IV	Dose modification CS1001 until resolved to ≤ Grade 1 Permanent discontinuation from the study
	myasthenia gravis	exam, • Nerve/muscle biopsy	methylprednisolone)	
Ocular toxicity	Photosensitivity, pain or dryness of the eyes, blurred vision, uveitis, iritis, episcleritis	• ophthalmic exam	Moderate (≤ Grade 2): topical steroids (1% prednisolone) Severe (≥ Grade 3): high dose systemic corticosteroids (2-4 mg/kg/day IV methylprednisolone)	Withhold the administration of CS1001 until resolved to $\leq$ Grade 1; if not resolved $\leq$ Grade 1 within 14 days with topical steroids or initiation of systemic treatment, permanent discontinuation from the study Permanent discontinuation from the study
Other irAEs, such as arthritis, pancreatitis, hemolytic anemia, adrenal			Moderate (Grade 2)	Withhold the administration of CS1001 until resolved to $\leq$ Grade 1
insufficiency, myasthenic syndrome, and rhabdomyolysis			Severe (≥ Grade 3)	Permanent discontinuation from the study

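### When a Grade 3 CS1001-related skin event has eased to Grade 2, Protocol 6.4.3 and 6.6.3 keep CS1001 on hold, the Appendix 3 dermatitis row ends the hold, and nothing says which prevails

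*Protocol*

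**What the plan says.** Five places in the Protocol bear on restarting CS1001 after a severe skin reaction.

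- **6.4.2 (suspension).** CS1001 is held for "Any Grade 3 skin, drug-related adverse event". The Grade 2 trigger in the same list is for non-skin events. A final item allows a hold at the investigator's discretion.
- **6.4.3 (resumption).** The general rule begins "Subjects may resume treatment with CS1001 when the CS1001-related AE(s) resolve to Grade" and sets the threshold at 1 or lower, or baseline, within 9 weeks of the scheduled dose. One of its exceptions begins "Subjects who have not experienced a Grade 3 drug-related skin AE may resume" and lets those subjects restart once skin toxicity is Grade 2 or lower.
- **6.4.4 (permanent discontinuation).** The prolonged Grade 3 rule reads "Any Grade 3 non-skin, drug-related adverse event lasting > 7 days, with the following exceptions", so it does not reach skin events.
- **6.6.3 (immune-related events).** "If the severity of AE is maintained at grade 1 or better, CS1001 treatment can be restarted". No skin exception is given. The section closes with a pointer: "For the identification, diagnosis, management and dose adjustment of irAE, please refer to APPENDIX 3". It also asks that immune-related events of Grade 3 or higher be reported to the sponsor as soon as possible.
- **14.3, Appendix 3, dermatitis row.** For the category that begins "Severe (Grade 3, >" (more than 30% of body surface area), CS1001 is withheld until the event is Grade 2 or lower.

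**The concern.** An investigator with a subject recovering from a Grade 3 skin reaction needs one answer to one question: at what grade may CS1001 be given again? The text gives two.

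Three things depend on the answer.

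- **Re-exposure.** The threshold decides how much residual toxicity is acceptable when CS1001 is given again after a severe reaction.
- **Length of the hold.** The hold counts toward the 9-week limit in 6.4, 6.4.3 and 6.4.4, beyond which treatment stops unless the medical monitor agrees otherwise. It also enters the relative dose intensity summarised under SAP 3.5.1.
- **Deviations.** 6.4 requires departures from its rules to be documented and communicated to the sponsor. With two opposed thresholds, neither the site nor the monitor can tell whether restarting at Grade 2 is a departure.

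**Working it through.** The plan states no figure on this point, so the check is a comparison of texts for one case.

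**Case.** A CS1001-related Grade 3 skin event, considered immune-related, first occurrence, now Grade 2. Skin toxicity at baseline was below Grade 2.

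**Step 1: does the restart question arise?** Yes. 6.4.2 requires the hold. The prolonged Grade 3 rule in 6.4.4 covers non-skin events only. 6.6.3 ends treatment for Grade 3 immune-mediated events that persist, worsen or recur; this event is improving and has not recurred.

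**Step 2: apply each restart rule.**

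| Protocol section | Condition for restart | Met at Grade 2? | Result |
|---|---|---|---|
| 6.4.3, general rule | Grade 1 or lower, or baseline | No | Hold |
| 6.4.3, skin exception | Grade 2 or lower, only if no Grade 3 skin event has occurred | Not available to this subject | Hold |
| 6.6.3 | Grade 1 or better | No | Hold |
| Appendix 3, dermatitis row | Grade 2 or lower | Yes | Hold ends |

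**Step 3: do the rules cover the same events?** Usually. The dermatitis row tells the reader to regard a skin reaction as immune-related unless another cause is found. A CS1001-related Grade 3 skin event will therefore normally fall under 6.4.3, 6.6.3 and Appendix 3 together.

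**Step 4: is the Appendix 3 threshold read correctly?** In the text version the table columns run together. The last line of the entry appears as "dose of 1-2 mg/kg/day Grade 2", where the dose belongs to the steroid column and the grade to the dose-modification column. Read down on its own, the dose-modification column says to withhold until Grade 2 or lower. The row's preceding entry agrees with this, since it continues dosing for dermatitis up to Grade 2.

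**Step 5: is there a precedence rule?** No. 6.6.3 sends the reader to Appendix 3 for dose adjustment but states its own Grade 1 threshold in the same section.

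**Step 6: how often might the case arise?** Protocol 2.4.1.2 reports the 29 subjects of the CS1001-101 dose escalation at the November 2018 cut-off. All immune-related events were Grade 1 or 2. The Grade 3 CS1001-related events named were platelet count decreased (1) and anemia (2), neither of them a skin event. If that list is complete, the count of Grade 3 skin events is 0 of 29, with an exact two-sided 95% upper limit of 1 − 0.025^(1/29) = 0.119, or about 12%. The earlier April 2018 summary in 4.2.2 gives immune-related events of Grade 1 to 3, but none of those it names is a skin reaction. Both summaries are for CS1001 alone, so the rate with the combination is unknown.

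**The case against.** The strongest reply is that Appendix 3 is the detailed guide for immune-related events and that 6.6.3 hands dose adjustment over to it. The pointer is real and favours Appendix 3 as the working table. It does not settle the matter, because 6.6.3 is itself the section on immune-related events and sets Grade 1 just before pointing to a table that says Grade 2.

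A second reply is that the rules are permissive, so a site that waits for Grade 1 breaches none of them. That is correct for the cautious site. A site that restarts at Grade 2 complies with Appendix 3 and departs from 6.4.3 and 6.6.3, and that is the case needing an answer.

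A third is that sponsor notification of Grade 3 immune-related events, and the room 6.4 leaves for clinical circumstance, will catch these cases. Notification does reduce the risk of unnoticed differences. It does not tell the sponsor which threshold to apply.

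Four stronger readings are tempting, and the documents do not support them.

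- **Sites will treat the same subject differently.** This is a foreseeable result, not something the documents report.
- **The choice of threshold changes the number of delays, and so the stop at a third delay.** Both rules hold CS1001 for the same event and record one delay. Only its length changes.
- **The 6.9% pruritus in CS1001-101 (2 of 29) shows that triggering events are to be expected.** Those events were Grade 1 or 2. Such skin events do not trigger a mandatory hold in 6.4.2, and the dermatitis row continues dosing for them.
- **The 6.4.3 skin exception applies to no one, because the skin trigger in 6.4.2 is Grade 3.** The exception can serve subjects held for another toxicity or at the investigator's discretion. The same list has an exception for Grade 2 fatigue, which needs no hold under 6.4.2 either. The fit between exception and trigger is worth checking, but it is not shown to be an error.

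The link to the tolerability endpoint is also indirect. That endpoint counts discontinuations and dose reductions, and CS1001 reduction is not permitted. The direct route is a hold that passes 9 weeks, and even then the medical monitor may allow treatment to continue.

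**Conclusion.** The inconsistency is real and is in the current text. For a Grade 3 CS1001-related skin event that has eased to Grade 2, 6.4.3 and 6.6.3 say hold, the Appendix 3 dermatitis row says the hold is over, and no passage ranks them.

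The difference is one CTCAE grade at restart. In time it may be larger: 6.6.3 places a steroid taper of at least 1 month after improvement to Grade 1, whereas Appendix 3 gives systemic steroids for this event and lifts the hold at Grade 2, possibly before that taper begins. What is affected is the timing of re-exposure, the length of the hold against the 9-week limit, and the classification of deviations.

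The conclusion assumes baseline skin toxicity below Grade 2 (otherwise the baseline clause in 6.4.3 would permit restart under that section) and an event that meets the row's Grade 3 description and is considered immune-related. Affected subjects may be few. The point should be fixed because it concerns re-exposure safety and costs little; it does not threaten the primary analysis.

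**What to change.** Reconcile 6.4.3, 6.6.3 and the Appendix 3 dermatitis row to a single restart criterion after a Grade 3 skin event. The choice of grade is for the clinical lead, and this review takes no position on it.

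At the same time, check the intended wording of the 6.4.3 skin exception against the Grade 3 trigger in 6.4.2, and add one sentence saying whether the body text or Appendix 3 governs when they differ. That sentence would also make clear which action counts as a deviation under 6.4.

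The cost is protocol wording through the usual amendment route. No analysis, sample size or data collection changes.
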